12. MEDICAL HISTORY

Medical History coded using MedDRA Version 25.0 will be listed for the exposed set.

13. MEDICATIONS

Medication usage coded using the WHO Drug Dictionary Version GlobalC3Mar22 will be listed for the exposed set.

‘Prior’ medications are medications which started and stopped prior to the first dose of study treatment.

‘Concomitant’ medications are medications which were taken during the treatment period, or specifically:

- o started after the first dose of study treatment or
- o started prior to the first dose of study medication and were continued after the first dose of study treatment

The percentage of participants using concomitant medications (any medication, any antipyretic and any antipyretic taken prophylactically, respectively) during the 7-day follow-up period and during the 28-day follow-up period will be summarized by group after each vaccination and overall.

14. STUDY MEDICATION EXPOSURE

Exposure to study treatment as the number of doses administered will be presented for each treatment, each step and all participants overall.

Document: \\dccar2dnetvnasc01p-lan1.quintiles.net\cp_ops\PROJECTS\Glaxo SmithKline\GSK205480_HAB61752\SAP
Author: PPD Version Number: 1.0
Version Date: 25OCT2022

Template No: CS_TP_BS016 – Revision 7
Effective Date: 01Nov2021

Reference: CS_WI_BS005

15. IMMUNOGENICITY ANALYSIS

The immunogenicity analysis will be based on the Per-protocol Set for analysis of immunogenicity. If, in any study group at any time point, the percentage of vaccinated participants with serological results excluded from the Per-protocol Set for analysis of immunogenicity is 10% or more, a second-line analysis based on the Full Analysis Set will be performed.

Numerical serology results will be derived from the content of IS.ISORRES in the SDTM dataset. For assays with a specific cut-off, the following derivation rules apply:

IS.ISORRES	Derived value
“NEG”, “-”, or “(-)”	cut-off/2
“POS”, “+”, or “(+)”	cut-off
“< value” and value is <= assay cut-off	cut-off/2
“< value” and value is > assay cut-off	value
“> value” and value is < assay cut-off	cut-off/2
“> value” and value is >= assay cut-off	value
“value” and value is < cut-off	cut-off/2
“value” and value is >= cut-off	value
All other cases	missing

The following derivation rules will apply in the context of LLOQ values:

- If baseline value is below LLOQ
 - 4-fold is defined as 4 times the LLOQ cut-off value
 - GMR is defined as within-participant GMR against LLOQ/2
- If baseline value is above or equal to LLOQ
 - 4-fold is defined as 4 times the baseline value
 - within-participant GMR is defined as within-participant GMR against the baseline value.

The following immunogenicity variables will be assessed:

Document: \\dccar2dnetvnasc01p-lan1.quintiles.net\cp_ops\PROJECTS\Glaxo SmithKline\GSK205480_HAB61752\SAP
Author: PPD Version Number: 1.0
Version Date: 25OCT2022

Template No: CS_TP_BS016 – Revision 7
Effective Date: 01Nov2021

Reference: CS_WI_BS005

Blood sampling timepoint		No. participants	Component
Type of contact and	Sampling timepoint		
Visit 1 (Day 1)	Pre-1 st vaccination	96	Anti-Vi antigen IgG (ELISA)
			Anti-O:2 IgG (ELISA)
			CCI [REDACTED]
Visit 3 (Day 29)	Post-1 st vaccination	96	Anti-Vi antigen IgG (ELISA)
			Anti-O:2 IgG (ELISA)
			CCI [REDACTED]
Visit 4 (Day 169)	Pre-2 nd vaccination	96	Anti-Vi antigen IgG (ELISA)
			Anti-O:2 IgG (ELISA)
			CCI [REDACTED]
Visit 5 (Day 176)	Post-2 nd vaccination 1	96	Anti-Vi antigen IgG (ELISA)
			Anti-O:2 IgG (ELISA)
			CCI [REDACTED]
Visit 6 (Day 197)	Post-2 nd vaccination 2	96	Anti-Vi antigen IgG (ELISA)
			Anti-O:2 IgG (ELISA)
			CCI [REDACTED]

A listing of collection dates and times for the immunogenicity variables will be presented for participants within each treatment group. For each component, the concentration/CCI [REDACTED] will be listed and summarized by treatment groups across all scheduled timepoints during entire study for each step.

For each study group, each step, at each timepoint that blood samples are collected for humoral immune response and for each component as measured by ELISA CCI [REDACTED]:

- Geometric mean concentrations/CCI [REDACTED] and their 95% CI at each timepoint will be calculated
- Within-subject Geometric mean ratio for Day 29 versus Day 1, Day 169 versus Day 1, Day 176 versus Day 1, Day 197 versus Day 1, Day 176 versus Day 169 and Day 197 versus Day 169 with their 95% CI will be tabulated
- Percentage of participants with ≥ 4 fold-increase in Anti-O:2 IgG antibody concentrations at, Day 29, Day 169, Day 176, and Day 197 compared to Day 1 baseline with their exact 95% CI will be calculated

For each study group, at each step, at each timepoint that blood samples are collected for humoral immune response and for each component as measured by ELISA

- The number and percentage of participants with Anti-Vi Ag IgG antibody concentrations $\geq 4.3 \mu\text{g/mL}^*$ and their 95% exact CI at each timepoint will be calculated

Document: \\dccar2dnetvnasc01p-lan1.quintiles.net\cp_ops\PROJECTS\Glaxo SmithKline\GSK205480_HAB61752\SAP
 Author: PPD [REDACTED] Version Number: 1.0
 Version Date: 25OCT2022

Template No: CS_TP_BS016 – Revision 7
 Effective Date: 01Nov2021

Reference: CS_WI_BS005

- The number and percentage of participants with Anti-Vi Ag IgG antibody concentrations $\geq 2.0 \mu\text{g/mL}^*$ and their 95% exact CI at each timepoint will be calculated

For step 2, at each timepoint that blood samples are collected for humoral immune response and for each component as measured by ELISA **CCI** as applicable:

- Unadjusted between-group ratio of GMC with 95% CI between full dose with Alum vs full dose without Alum will be computed for each component specific IgG, visit, and administration
- Adjusted between-group ratio of GMC with 95% CI between full dose with Alum vs full dose without alum will be computed for each specific IgG, visit, and administration

The above tabulations may be performed by LLOQ status at baseline (above or equal to cut-off versus below the cut-off) for all 2 components, data permitting [if at least 6 participants are available in these sub-group and in at least one active arm].

Only for Anti-Vi antigen IgG antibody component the above tabulations may be performed by Anti-Vi antigen IgG antibody concentrations status at baseline as measured by ELISA ($\geq 4.3 \mu\text{g/mL}^*$ and $< 4.3 \mu\text{g/mL}^*$, $\geq 2.0 \mu\text{g/mL}^*$ and $< 2.0 \mu\text{g/mL}^*$), data permitting [if at least 6 participants are available in these sub-group and in at least one active arm].

Linear mixed model with repeated measures (MMRM) will be used to perform pairwise comparison between full dose with Alum and full dose without Alum at Day 29, Day 169, Day 176 and Day 197. The model will use fixed effects for treatment, time point, treatment*time point and baseline immunogenicity value as covariate, and a repeated time point effect within a participant under an unstructured covariance matrix. Variance between the groups will not be considered equal unless the assumption leads to convergence issues. Additional covariance structures and suitable transformation (e.g., log) may be explored to attain convergence and meet model assumptions, respectively.

```
proc mixed data=indsn;
by parameter;
class subjid trta avisit;
model aval= trta avisit trta*avisit baseline/ddfm=satterth;
repeated avisit/subject=subjid type=un group=trta;
lsmeans trta*avisitn/pdiff cl alpha=0.05;
run;
```

* The IgG against Vi antigen will be determined using ELISA and the results will be presented in EU/mL unit, which may be further converted to $\mu\text{g/mL}$, based on correlation with concentration of the standard calibrated against the international standard/another standard already calibrated.

CCI

Document: \\dccar2dnetvnasc01p-lan1.quintiles.net\cp_ops\PROJECTS\Glaxo SmithKline\GSK205480_HAB61752\SAP
Author: PPD Version Number: 1.0
Version Date: 25OCT2022

Template No: CS_TP_BS016 – Revision 7
Effective Date: 01Nov2021

Reference: CS_WI_BS005

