6.6. COMMON CALCULATIONS

For quantitative safety measurements (e.g. vital signs, laboratory parameters), change from baseline will be calculated as:

- Observed Value (after baseline) – Baseline Value

For immunogenicity measurements, fold change from baseline will be calculated as:

Document:	\dccar2dnetvnasc01p-lan1.quintiles.net\cp_ops\PROJECTS\Glaxo SmithKline\GSK205480_HAB61752\SAP		
Author:	PPD	Version Number:	1.0

Template No: CS_TP_BS016 – Revision 7
Effective Date: 01Nov2021

Reference: CS_WI_BS005

- Test Value (after baseline)/Baseline Value

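### SAP Section 15 lets a result reported as below X count as reaching any responder limit up to X; a one-sentence rule would close the gap

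*SAP*

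**What the plan says.** SAP Section 15 states that "Numerical serology results will be derived from the content of IS.ISORRES in the SDTM dataset" and gives a table of strings and derived values. Two rows cover results reported as less than a number:

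- "< value” and value is <= assay cut-off": derived as half the cut-off.
- "< value” and value is > assay cut-off": derived as the value itself.

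The same section then tabulates "The number and percentage of participants with Anti-Vi Ag IgG antibody concentrations" at or above 4.3 µg/mL and at or above 2.0 µg/mL, and the percentage with at least a 4-fold rise in anti-O:2 IgG over Day 1. All three limits are inclusive. The 4-fold target is 4 × LLOQ if the baseline is below LLOQ, and 4 × baseline otherwise. SAP 6.6 defines fold change as "Test Value (after baseline)/Baseline Value".

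Three other sections touch on low or missing results. SAP 6.1 assigns half the cut-off, but only to results below the cut-off. SAP 7.1 refers missing immunogenicity data back to Section 15. The readable part of SAP 7.2.7 leaves the cut-off to the laboratory; the rest of that section is redacted. Nothing readable keeps a `< X` result above the cut-off out of the responder counts.

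**The concern.** A result reported as `< X` is left-censored: the true concentration lies somewhere below X. Replacing it by X gives it the highest number consistent with the report. With an inclusive limit, that number passes any limit not above X, so the report that the sample is below X becomes evidence that it reached the limit.

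The responder rates are where this bites. Protocol 9.2.2 names the anti-O:2 4-fold rise as the seroresponse measure and says that results in the two full-dose groups will guide later studies. With about 21 evaluable participants per full-dose group, one participant counted on the wrong side is visible in the percentage.

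**Working it through.** **The plan's own figure.** Protocol 9.2.2 assumes 12% dropout from 24: 24 × 0.88 = 21.12, so 21 evaluable. Two-sided 95% Clopper-Pearson intervals for 10 to 18 responders of 21 reproduce all nine rows of Table 15, for example 10/21 = 47.6% (25.7–70.2) and 18/21 = 85.7% (63.7–97.0).

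**Anti-Vi limits.** The documents give no numerical cut-off. Assume 1.0 µg/mL and apply the Section 15 table:

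| Reported | Derived | Counted ≥2.0 | Counted ≥4.3 | What the report supports |
|---|---|---|---|---|
| `<1.0` | 0.5 | no | no | below both |
| `<2.0` | 2.0 | yes | no | below both |
| `<3.0` | 3.0 | yes | no | 2.0 unknown; below 4.3 |
| `<4.3` | 4.3 | yes | yes | 2.0 unknown; below 4.3 |
| `<5.0` | 5.0 | yes | yes | both unknown |

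Assumed cut-offs of 0.1, 0.5 and 1.9 give the same counts. At 2.5, `<2.0` becomes 1.25 and is not counted, but `<3.0` still counts as at least 2.0, and `<4.3` and `<5.0` still count as at least 4.3.

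There are three cases:

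1. X below the limit: correctly not counted.
2. X equal to the limit: counted, and certainly wrong.
3. X above the limit: counted, with true status unknown.

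**4-fold rise, censored follow-up.** Assume LLOQ = cut-off = 1 EU/mL and a baseline below LLOQ. The target is 4 × 1 = 4. A follow-up of `<4` becomes 4 and `<5` becomes 5; both are counted as responses.

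**4-fold rise, censored baseline.** A Day 1 result of `<4` becomes 4, so the target is 4 × 4 = 16. If the true baseline was below LLOQ, the target would have been 4. A follow-up of 16 or more is a certain response, because the true baseline is below 4. A follow-up below 4 is a certain non-response. Between 4 and 16 the bound does not settle the answer. Here X is the conservative choice.

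**Size per participant.** One reclassification moves a rate by 100/n points: 4.8 at n = 21, 4.2 at n = 24, 8.3 at n = 12 and 16.7 at n = 6 (the last three are randomised group sizes). At n = 21, 10/21 = 47.6% (25.7–70.2) becomes 11/21 = 52.4% (29.8–74.3), and 0/21 = 0% (0–16.1) becomes 1/21 = 4.8% (0.1–23.8).

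**Geometric means: replace or delete?** Assume 20 participants with GMC 20, plus one reported as `<5` whose true value is 2. With that participant's value v, the GMC is 20 × (v/20)^(1/21).

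- True value, v = 2: 17.9.
- SAP rule, v = 5: 18.7.
- Half an assumed cut-off of 1, v = 0.5: 16.8.
- Result set to missing: 20.0.

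In this example deletion misses by 2.1 and the SAP rule by 0.8. X and half the cut-off bracket the truth.

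**The case against.** The strongest reply is that the row may never be used. The table also has positive/negative rows that do not suit a quantitative ELISA, so it reads as a generic list of possible strings. Low ELISA results would ordinarily be reported against the cut-off and fall in the half-cut-off row, which is not in dispute. This stands, and it limits the point to a minor one.

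A reader might infer more than the documents support:

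- **That rates and GMCs in this trial are inflated.** Nothing says the laboratory will report less than a number above its cut-off, or how often.
- **That outright reversals are likely.** A reversal needs the bound to equal the limit exactly. The table works on the original result string, and SAP 15 says anti-Vi results are presented in EU/mL and may be converted to µg/mL. A bound landing on exactly 4.3 or 2.0 would be coincidence. A bound above the limit is the more realistic case, and there the count is unsupported but not known to be false.
- **That true anti-O:2 responders will be lost through Day 1 results.** Protocol 4.2.3 expects no pre-existing antibodies, and Protocol 5.2 excludes prior typhoid vaccination and recent travel to the listed endemic countries. Censored Day 1 results above the cut-off should be rare.
- **That the row "> value” and value is < assay cut-off" is a second error needing repair.** It can give a number below the reported bound, but it requires a laboratory to report greater than a number under its own cut-off. No effect on any endpoint can be shown.
- **That these results should be set to missing.** They are low results, so deleting them can raise a GMC more than the present rule does, and dropping them from the denominator can raise responder rates. SAP 11.2 also lists unavailable post-vaccination serology among the reasons for leaving the per-protocol set.

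Two limits on the evidence: part of SAP 7.2.7 is redacted, and any laboratory retest rules would sit in documents not available here.

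**Conclusion.** The point holds as a minor correction to secondary, descriptive endpoints. As written, SAP 15 counts a post-vaccination `< X` result above the cut-off as reaching every responder limit up to X. The count is certainly wrong if X equals the limit and unsupported if X is higher. The effect is 4.8 points per affected participant in a full-dose group of 21. The total is unknown and may be nil.

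That conclusion rests on the readable text alone. The numerical cut-offs are assumptions, but the three-case pattern does not depend on which one is chosen. No claim is made that any reported GMC, GMR or responder rate will be materially biased.

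**What to change.** Add to SAP 15:

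1. A `< X` result above the cut-off is never counted as reaching an anti-Vi limit or a 4-fold target on the strength of its bound. The participant stays in the denominator as a non-responder.
2. If the Day 1 result is `< X`, keep X as the baseline for the 4-fold count, since a rise to at least 4X is then a certain response. Flag participants whose status the bound does not settle.
3. Keep the derived value for GMCs and GMRs; do not set these results to missing. Report the number of such results by group and timepoint. If there are any, add a sensitivity analysis with half the cut-off in place of X.

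Leave the other rows of the table unchanged.

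The cost is a short SAP addition, one programming flag and a count in the output. The downside is slightly lower responder rates if such results occur, because a participant whose bound exceeds the limit may truly have reached it. If none occur, nothing changes.

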9. STATISTICAL CONSIDERATIONS

9.1. Statistical hypotheses

No specific statistical hypotheses will be tested in this study. All analyses of safety and immunogenicity will be descriptive. Results of this study will inform the planning of subsequent studies and selection of candidate vaccine formulation.

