6.1. SUMMARY STATISTICS

For qualitative variables, the population size (N for sample size and n for available data) and the percentage (of available data) for each class of the variable will be presented. Quantitative variables will be summarized using descriptive statistics, including N (with data available), mean, standard deviation (SD), coefficient of variation (CV%), median, Q1, Q3, minimum, and/or maximum values. Geometric mean will be included for immunogenicity parameters, where applicable. Coefficient of variation will not be presented for change from baseline results.

The exact two-sided 95% CIs for a proportion within a group will be calculated using the Clopper-Pearson exact method.

The geometric mean antibody concentrations (GMCs) and CCI [REDACTED] calculations will be performed by taking the anti-log of the mean of the log10 titer transformations. Confidence interval for geometric means will be derived by raising 10 to the confidence interval associated with mean of log10 values i.e., CI of geometric mean = $10^{(CI \text{ for the mean of log10 values})}$. All participants with valid data will be considered. Participants whose antibody titers are below the cut-off of the assay will be given an arbitrary value of half the cut-off for the purpose of GMC/CCI [REDACTED] calculation.

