6.3. PRECISION

Safety data (vital signs, laboratory parameters) and immunogenicity data will be reported to the same precision as the source data.

For the reporting of descriptive statistics, the mean, median, Q1, Q3, standard deviation, standard error and confidence intervals will be presented to one digit more precision than the source data. The minimum and maximum will be presented to the same precision as the source data. Coefficient of variation (%) will always be reported to 1 decimal place. P-values, if any, shall be reported to four decimal places or as <0.0001.

The number of decimals used when displaying geometric mean concentrations (GMC)/CCI and their confidence limits is shown in the following table:

GMC/ CCI value	Number of decimals to display
<0.1	3
>=0.1 and <10	2
>=10 and <1000	1
>=1000	0

When multiple categories of CCI/GMC values are present in the same table, the number of decimals displayed should match that of the smallest category (i.e., the one with the higher number of decimals). GMR (geometric mean ratios) or CCI/GMC ratios and their confidence limits will be displayed with 2 decimals regardless of the actual values.

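### SAP 15 promises an adjusted GMC ratio, but its only adjusted model has no log scale and no back-transformation, and makes the log optional

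*SAP*

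**What the plan says.** SAP Section 15 lists two Step 2 comparisons of the full-dose groups, an unadjusted GMC ratio and an adjusted one: "Adjusted between-group ratio of GMC with 95% CI between full dose with Alum vs full dose without alum will be computed". Two other sections fix what a GMC is and how a ratio is shown.

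- SAP 6.1, on GMCs: "calculations will be performed by taking the anti-log of the mean of the log10 titer transformations". The interval is back-transformed in the same way. Section 7.2.7 repeats the log and inverse-log rule.
- SAP 6.3, on display: "GMC ratios and their confidence limits will be displayed with 2 decimals regardless of the actual values".

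The only model with a covariate is the MMRM in Section 15. It compares the two full-dose groups at Days 29, 169, 176 and 197, with the baseline value as covariate and a separate unstructured covariance per group. The key statement is "model aval= trta avisit trta*avisit baseline/ddfm=satterth", and the estimates are requested by "lsmeans trta*avisitn/pdiff cl alpha=0.05". On scale, the text says only that a "suitable transformation (e.g., log) may be explored to attain convergence and meet model assumptions, respectively".

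**The concern.** The promised quantity lives on the log scale, while the printed model is on whatever scale `aval` has. No text says that `aval` or `baseline` is a log, and no step turns a difference into a ratio. Because the log is presented as an option, the stated default is the untransformed concentration, and the scale would be settled after seeing how the model fits.

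The trial is descriptive and this is not a primary endpoint. Still, Protocol 9.1 says: "Results of this study will inform the planning of subsequent studies and selection of candidate vaccine formulation". This is the only adjusted comparison of the two full-dose formulations in the visible text. At stake are the quantity reported for the adjuvant effect and the precision of its interval.

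**Working it through.** The documents give no GMC ratio, SD or correlation, so there is no planned figure to reproduce. The one numerical input they supply is the evaluable number per full-dose group in Protocol 9.2.2: 24 × (1 − 0.12) = 21.12, which agrees with the stated 21. All SDs, correlations and true ratios below are assumptions.

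**1. What the code estimates.** An LS-mean difference on `aval` is a difference in adjusted arithmetic means, in assay units. On log10 values the same contrast d gives the promised quantity: ratio = 10^d, with CI = 10^(limits of d).

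**2. Does a raw difference determine the GMC ratio?** For lognormal data with log10 SD s, arithmetic mean = GMC × k, where k = exp((ln 10 × s)² / 2). With s = 0.5 in both arms, k = exp((2.3026 × 0.5)² / 2) = 1.94. A raw difference of 10 units then implies a GMC ratio of (g0 × k + 10) / (g0 × k), where g0 is the without-Alum GMC:

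| g0 | Implied GMC ratio |
|---|---|
| 2 | 3.58 |
| 5 | 2.03 |
| 10 | 1.52 |
| 20 | 1.26 |

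**3. Would dividing the two raw means repair it?** Only if the log-scale SDs are equal, and the SAP by default does not treat the group variances as equal. The arithmetic-mean ratio is GMC ratio × exp(((ln 10 × s_A)² − (ln 10 × s_B)²) / 2), with A the Alum arm. With s_A = 0.75 × s_B:

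| s_B | True GMC ratio 1.00 appears as | True GMC ratio 2.00 appears as |
|---|---|---|
| 0.30 | 0.90 | 1.80 |
| 0.45 | 0.79 | 1.58 |
| 0.60 | 0.66 | 1.32 |

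**4. Precision.** The simulation followed the structure of the SAP model: 21 per arm, four post-baseline visits, a common baseline slope, unstructured covariance by group, complete data, 8,000 runs per setting. It assumed correlation 0.5 between visits and 0.3 with baseline, baseline log10 SD 0.4 and a true GMC ratio of 2.5. A single-visit Welch interval without covariate (40,000 runs) is shown beside it. Entries are the percentage of runs in which the Day 29 95% CI excludes no difference.

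| log10 SD | Model, log | Model, raw | Welch, log | Welch, raw |
|---|---|---|---|---|
| 0.3 | 99.3 | 96.4 | 98.7 | 95.6 |
| 0.4 | 91.4 | 73.3 | 88.4 | 72.2 |
| 0.5 | 74.4 | 46.3 | 71.3 | 45.6 |
| 0.6 | 58.8 | 27.5 | 55.5 | 27.3 |

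The loss in the model is 2.9, 18.1, 28.1 and 31.3 points.

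**5. False positives.** With equal GMCs, the raw-scale model interval excludes zero in 3.1% of runs (SDs 0.5/0.5), 4.2% (0.5/0.4) and 5.6% (0.6/0.4). There is no material inflation.

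**6. The code itself.** CLASS, MODEL and REPEATED use `avisit`, whereas LSMEANS names `trta*avisitn`. That effect is not in the model, so the statement cannot return the estimates as printed.

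**The case against.** The estimand is worded correctly, and SAP 6.1 and 7.2.7 say how GMCs are computed. A programmer asked for a GMC ratio has to use logs, so this may be incomplete wording and nothing worse. `aval` is a generic name and could already hold log10 values. Text is blacked out in Section 7.2.7 and after the model in Section 15, and the table templates are not visible. The SAP never says that the MMRM is the source of the adjusted ratio. These points limit certainty. They do not settle the matter, because listing the log as something to explore makes little sense if the response is already logged, and 6.1 and 7.2.7 are not tied to the model.

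A second argument is that the raw-scale losses arise only if nobody checks the fit. In the single-visit set-up, a Shapiro-Wilk check rejects normality of the raw residuals in 96% of runs at SD 0.3 and at least 99.5% at 0.4 to 0.6. Switching to logs on rejection recovers essentially the whole log-scale performance. That is fair, but the SAP names no check and says only that a transformation may be tried. A change of scale also changes the quantity estimated, so it should not hinge on a diagnostic.

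Third, the unadjusted GMC ratio remains. On the log scale it falls only 0.6 to 3.3 points short of the adjusted model in the table above. The table in Protocol 9.4.2 contains no between-group ratio, and Protocol 9.2.2 discusses full-dose decisions alongside the anti-O:2 4-fold response. All of this stands and keeps the point below a primary-analysis defect.

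**Conclusion.** The concern holds. In the visible text, the stated default model gives an adjusted difference in arithmetic means, while the SAP promises an adjusted ratio of geometric means. The two are not interchangeable, and the adjusted result could not be read beside the unadjusted ratio. If the raw scale were kept, the precision loss would be small at a log10 SD of 0.3 and large at 0.5 to 0.6. The error rate under no difference is not a concern.

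The conclusion that the quantity is wrong as written needs no assumed SD. It does rest on two readings: that the MMRM is the source of the adjusted ratio, and that `aval` holds untransformed concentrations. The sizes rest on lognormal data and the assumed SDs, correlations and ratio. This should be fixed before the analysis is run. It does not affect the primary safety endpoints, the per-group GMCs, the within-subject ratios or the seroresponse rates.

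**What to change.** In SAP Section 15:

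- State that the MMRM is the source of the adjusted between-group GMC ratio.
- Prespecify log10(concentration) as the response and log10(Day 1 concentration) as the covariate. Values below the cut-off are already set to half the cut-off, so the log is defined.
- Delete the wording that makes the transformation optional.
- Change the LSMEANS term to `trta*avisit`.
- With two groups and four visits there are 8 cells and 8 × 7 / 2 = 28 pairwise differences. Report only the four same-visit contrasts (Days 29, 169, 176 and 197), as 10^(difference) with 10^(CI limits).

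The cost is a few lines of SAP text and code. No further data are needed and nothing changes for participants.
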